## 1.6 Correlative Studies

We will collect peripheral blood samples serially to facilitate analyses such as mutation analysis of circulating free tumor DNA and quantitation of circulating cytokines and EGFR ligands including epiregulin and amphiregulin. There is a growing body of evidence that one mechanism of resistance to anti-EGFR Mab therapy is the emergence of mutations or amplification in key components of the MAPK signaling pathways, including in *EGFR*, *KRAS*, and *NRAS*. In addition, we have retrospective data indicating that treatment with anti-EGFR Mabs is associated with differential levels of cytokines and growth factors, including epiregulin and TRAIL. These different resistance mechanisms, especially circulating TRAIL levels, are likely to have consequences on immune activation and response, and the association of each of these markers with RR, PFS, and OS will be determined.

We will also plan to perform peripheral blood immune monitoring, such as assessment of ADCC and T cell activity, and can consider sequencing peripheral blood mononuclear cells for FcγRIIa and FcγRIIIa polymorphisms. There have been conflicting studies regarding the prognostic utility of FcγRIIa or FcγRIIIa polymorphisms and anti-EGFR Mab efficacy, though the largest study to date showed no significant association in *KRAS* wild-type subjects with mCRC. Since these factors may affect immune activation, sequencing for polymorphisms in *FCGR2A* and *FCGR3A* may be informative. Additionally, isolation of T cells and NK cells from subject-derived PBMCs to perform ex vivo ADCC assays and interferon γ release assays would provide important data on the activation of adaptive and innate immune cells.

Additionally, we will include optional serial tumor biopsies to identify potential biomarkers for immune checkpoint inhibitors and anti-EGFR antibodies. These could include integrated genomic analysis with multiplex next generation DNA and RNA sequencing for baseline mutation analysis, and gene expression analyses. This approach can also facilitate sequencing of low-diversity B cell and T cell receptors, both at baseline and serially in subjects who opt to undergo serial biopsies, which may aid in discovery of future potential targets for intervention.

Finally, we will collect stool specimens to identify gut microbial composition at baseline and at first restaging. Several studies have shown significant associations between gut microbial dysbiosis and lack of efficacy of immune checkpoint inhibitors, and we will perform exploratory studies to determine the association between baseline gut microbiome and efficacy of therapy.

## 2.0 STUDY OBJECTIVES

### 2.1 Primary Objective

To evaluate the clinical efficacy of panitumumab/nivolumab/ipilimumab or panitumumab/nivolumab therapy in subjects with unresectable refractory *KRAS/NRAS/BRAF* wild-type MSS mCRC, by determining overall response rate (ORR) at 12 weeks by RECIST 1.1 criteria.

## 2.2 Secondary Objectives

- 2.2.1 To determine the best overall response associated with panitumumab/nivolumab/ipilimumab or panitumumab/nivolumab therapy in subjects with unresectable refractory *KRAS/NRAS/BRAF* wild-type MSS metastatic colorectal adenocarcinoma based on both RECIST1.1 and irRECIST criteria.
- 2.2.2 To determine the overall response rate (ORR) associated with panitumumab/nivolumab/ipilimumab or panitumumab/nivolumab therapy in subjects with unresectable refractory *KRAS/NRAS/BRAF* wild-type MSS metastatic colorectal adenocarcinoma at 12 weeks by irRECIST criteria.
- 2.2.3 To determine PFS associated with panitumumab/nivolumab/ipilimumab or panitumumab/nivolumab therapy in subjects with unresectable refractory *KRAS/NRAS/BRAF* wild-type MSS metastatic colorectal adenocarcinoma based on both RECIST 1.1 and irRECIST criteria.
- 2.2.4 To determine OS of subjects with unresectable refractory *KRAS/NRAS/BRAF* wild-type MSS metastatic colorectal adenocarcinoma treated with panitumumab/nivolumab/ipilimumab or panitumumab/nivolumab therapy.
- 2.2.5 To determine the duration of response of subjects with unresectable refractory *KRAS/NRAS/BRAF* wild-type MSS metastatic colorectal adenocarcinoma treated with panitumumab/nivolumab/ipilimumab or panitumumab/nivolumab therapy based on both RECIST1.1 and irRECIST criteria
- 2.2.6 To evaluate the toxicity of panitumumab/nivolumab/ipilimumab in subjects with unresectable refractory *KRAS/NRAS/BRAF* wild-type MSS mCRC, by determining the number of treatment-emergent grade 3 and 4 toxicities as defined by National Cancer Institute - Common Terminology Criteria for Adverse Events (NCI CTCAE v4.03).

## 2.3 Exploratory Objectives

### 2.3.1

[REDACTED]

[REDACTED]

[REDACTED]

[REDACTED]

[REDACTED]

[REDACTED]

[REDACTED]

[REDACTED]

[REDACTED]

## 2.4 Endpoints

### 2.4.1 Primary Endpoint

ORR is defined as the percentage of subjects with unresectable refractory *KRAS/NRAS/BRAF* wild-type MSS mCRC who achieve a complete response or a partial response (CR+PR) by 12 weeks to panitumumab/nivolumab/ipilimumab or panitumumab/nivolumab therapy per RECIST 1.1 criteria.

### 2.4.2 Secondary Endpoints

**2.4.2.1** The best overall responses for both RECIST 1.1 and irRECIST are defined as the best response achieved across all time points prior to progression (for example, a subject who has SD at first assessment, PR at second assessment, and PD on last assessment has a best overall response of PR). Please Note: In the case of SD, measurements must have met the SD criteria at least once after study entry at a minimum interval of 12 weeks from initiation of treatment.

**2.4.2.2** The immune-related response rate is defined as the percentage of subjects with unresectable refractory *KRAS/NRAS/BRAF* wild-type MSS mCRC who achieve a CR+PR by 12 weeks to panitumumab/nivolumab/ipilimumab or panitumumab/nivolumab therapy per irRECIST criteria. (See section 6.7.5.1)

**2.4.2.3** Assessment of immune-related PFS is defined as starting from the first day of treatment or Day 1 (D1) until the event of disease progression as defined by irRECIST, or death from any cause in subjects with unresectable refractory *KRAS/NRAS/BRAF* wild-type MSS mCRC (See section 6.7.5.1). Any subject that has not had a documented event at the time of analysis will be censored. Assessment of PFS (as defined by RECIST 1.1) is defined from D1 of treatment until the event of disease progression occurs or death from any cause in subjects with unresectable refractory *KRAS/NRAS/BRAF* wild-type MSS mCRC. Any

October 01,,  
2020

subject that has not had a documented event at the time of analysis will be censored.

- 2.4.2.4 OS is defined as the time from D1 of treatment until death from any cause. Any subject that has not died by the analysis date will be censored.
- 2.4.2.5 The duration of response as defined by RECIST 1.1 will be defined as the time elapsed from first scan documenting partial response or complete response until the event of disease progression occurs. Any subject that has not had a documented progression at the time of analysis will be censored. The duration of response as defined by irRECIST will be defined as the time elapsed from first scan documenting partial response or complete response until the event of disease progression occurs. Any subject that has not had a documented progression at the time of analysis will be censored.
- 2.4.2.6 Treatment-related adverse events will be assessed per NCI-CTCAE v4.03.

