
If DLTs occur in no more than one subject in the first 6 subjects treated during the 12 week assessment period in the first safety cohort, then the trial would continue enrolling subjects to the remainder of the first stage of the phase II portion to complete enrollment to 32 subjects to assess efficacy of panitumumab, ipilimumab and nivolumab (3-drug combination). This would then be followed by interim analysis to determine whether the second stage would merit enrollment. If the 3-drug combination is not well tolerated, then 6 additional subjects will be enrolled into safety cohort 2 and receive panitumumab and nivolumab (2-drug combination). If no more than one subject experiences a DLT in safety cohort 2, then the trial will continue enrolling subjects into the phase II portion and the 2-

October 01,,  
2020

drug combination of panitumumab and nivolumab will be evaluated efficacy. Subjects may continue combination treatment as long as they are benefitting from therapy until disease progression, unacceptable toxicity or withdrawal for other reasons as deemed necessary by the investigator.

DLT definitions applicable to the safety assessment run-in are defined in section 4.2. Subjects will undergo disease evaluation every 6 weeks for the first year, and will continue on this disease assessment schedule if they are at least stable but have less than a CR. If subjects continue on study after one year with a CR, then disease evaluations may occur every 12 weeks from that point forward.

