## 6.0 EVALUATIONS AND ASSESSMENTS

### 6.1 Time and Events Table

Assessment	Pre-Study 	D1  Cycle 1	D15  Cycle 1	D29  Cycle 1	D1  Cycle 2	D15  Cycle 2	D29  Cycle 2	D1  Cycle 3-N	D15  Cycle 3-N	D29  Cycle 3-N	End of Treatment 	30-day Follow up 	100-day Follow up 	Long term Follow up 
Informed Consent	X													
History 	X	X	X	X	X	X	X	X	X	X	X	X		
Physical exam	X	X	X	X	X	X	X	X	X	X	X	X		
Performance Status	X	X	X	X	X	X	X	X	X	X	X			
Tumor measurement 	X							X 						
Pregnancy test 	X	X 			X 			X 			X 	X 		
Hematology 	X	X	X	X	X	X	X	X	X	X	X			
Serum Chemistries	X	X	X	X	X	X	X	X	X	X	X			
TSH, Free T3/T4 	X				X			X			X			
ACTH/Amylase/Lipase 	X				X			X			X			
CEA 	X				X			X			X			
Toxicity Assessment	X	X	X	X	X	X	X	X	X	X	X	X	X	X
Concomitant Meds 	X	X	X	X	X	X	X	X	X	X	X	X		
Ipilimumab IV (if DL1 safe) 		X			X			X						
Nivolumab IV 		X	X	X	X	X	X	X	X	X				
Panitumumab IV 		X	X	X	X	X	X	X	X	X				
Request archival or Perform mandatory biopsy	X 													
Blood sample 		X			X			X			X			
Stool specimen	X							X 						
On treatment Tumor biopsy (Optional; goal n=15)	X			X 										
Survival analysis													X	X

1. Radiological assessments and physical exam may be performed within 4 weeks prior to day 1 of treatment. Other evaluations except for pregnancy test must be performed within 3 weeks prior to Cycle 1 Day 1 (C1D1) of treatment. Serum or urine  $\beta$ -HCG must be performed **within 24 hours prior** to first dose of study medication for women of child-bearing potential. Other screening labs performed within 72 hours prior to Cycle 1 Day 1 do not need to be repeated on C1D1.
2. Treatment cycles are to be repeated every 42 days until progression. A window of +/- 3 days applies to all study visits unless otherwise specified. While the treatment window is +/- 3 days, a minimum of 12 days must pass before the next dose of nivolumab.

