3. The end of treatment visit should only occur when subjects permanently stop study treatment. Subjects who have an ongoing  $\geq$  grade 2 or serious AE (SAE) at this visit will continue to be followed until the event is resolved or deemed irreversible by the investigator. The 30-day (+/- 7 days) follow up visit after stopping study treatment should be performed to check for ongoing toxicity. Subsequently, subjects should be contacted by telephone at approximately 100 days (+/- 7 days) after discontinuing study treatment for the emergence of SAEs (including checking for pregnancy) and to ensure contraceptive guidelines are followed as stipulated in inclusion criteria 3.1.11 and 3.1.12. Subsequent long-term follow-up for survival, defined as every 90 days thereafter (+/- 15 days) for up to 3 years or until death (whichever is first) may be conducted via telephone or chart review and/or clinic visit. Long term survival follow up will be limited to history of any subsequent cancer treatments, an assessment of any SAEs (including checking for pregnancy) considered to be possibly or probably related to study treatment until resolution, and survival status.
4. Complete history at baseline only, thereafter focused history on symptoms/toxicity; physical exam to include height (baseline only), examination of the skin, weight, and vital signs. Note that starting with cycle 7, only include assessment by physician on days 15 and 29 if clinical signs and symptoms warrant MD consult
5. Tumor imaging should remain consistent throughout study and should include those thought by investigator to best capture status of disease. Disease assessments should include contrasted computed tomography (CT) of the chest and either contrasted CT of abdomen and pelvis or MRI of abdomen and pelvis. Repeat tumor imaging every 12 weeks (+/- 1 week).
6. Urine or serum  $\beta$ -HCG must be performed within 24 hours prior to first dose of study medication for women of child-bearing potential. The test result must be confirmed as negative prior to dosing with study medication. A serum or urine pregnancy test must be repeated every 6 weeks while receiving study medications and repeated approximately 30 days after discontinuing the study medications.

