#### 6.3.5 D1 of Cycle 3-N

Focused history and physical examination (including weight) /

ECOG Performance Status (see appendix 11.1)

Laboratory evaluations:

- Hematology: CBC with differential
- Complete Metabolic Panel (plus Mg and Phosphorus)
- TSH/Free T3/Free T4
- ACTH/Amylase/Lipase
- CEA
- Serum or urine pregnancy test in women of childbearing potential (within 24 hours of dosing with study medications)
- Blood sample for correlative studies

Concomitant medication(s): All concomitant medications will be recorded.

Tumor evaluation: Contrasted computed tomography (CT) of the chest, and either contrasted CT of abdomen and pelvis or MRI of abdomen and pelvis on cycles 3, 5, 7, etc. **Note:** Repeat tumor imaging every 12 weeks (+/- 1 week).

Stool Specimen: Collect stool specimen from patients as described in Laboratory manual +/- 7 days from Day 1 of Cycle 3 only.

Toxicity evaluation: Use NCI CTCAEv4.03 for notation of any baseline toxicity

Administer Study Medications according to Safety Cohort 1 or 2 schedule as depicted in sections 4.3.10 and 4.3.2, respectively

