### 6.7.4 Evaluation of Non-Target Lesions using RECIST 1.1 Criteria

Complete response (CR)—Disappearance of all non-target lesions and normalization of tumor marker levels. All LN must be non-pathological in size (<10mm short axis).

Non-complete response (non-CR)/non-progression (non-PD)—Persistence of one or more non-target lesion(s) or/and maintenance of tumor marker level above the normal limits.

Progressive disease (PD)—Appearance of one or more new lesions and/or unequivocal progression of existing non-target lesions.

**NOTE:** Any progressive disease as defined by RECIST1.1 in subjects that are asymptomatic without signs or symptoms of impending visceral crisis SHOULD be confirmed by repeat scan to rule out "tumor flare" (pseudoprogression) related to immune response. In these subjects and per MD discretion, study therapy should be continued in these subjects until the repeat scan is performed approximately 4 weeks but no more than 6 weeks later. If PD is confirmed, subjects will be withdrawn from study. If tumor flare confirmed, subjects may continue therapy as per protocol. Subjects that have clear progressive disease as defined by RECIST 1.1 should be withdrawn from treatment and a repeat scan is not necessary.

**6.7.4.1 Evaluation of Best Overall Response** - The best overall responses for both RECIST 1.1 and irRECIST are defined as the best response achieved across all time points prior to progression (for example, a subject who has SD at first assessment, PR at second assessment, and PD on last assessment has a best overall response of PR). Please Note: In the case of SD, measurements must have met the SD criteria at least once after study entry at a minimum interval of 12 weeks from initiation of treatment.

The best overall response will be defined according to the following table:

Overall Response First Time Point	Overall Response Subsequent Time Point	BEST Overall Response
CR	CR	CR
CR	PR	SD, PD, or PR 
CR	SD	SD provided minimum criteria for SD duration met, otherwise, PD
CR	PD	SD provided minimum criteria for SD duration met, otherwise, PD
CR	NE 	SD provided minimum criteria for SD duration met, otherwise, NE 
PR	CR	PR
PR	PR	PR
PR	SD	SD
PR	PD	SD provided minimum criteria for SD duration met, otherwise, PD
PR	NE 	SD provided minimum criteria for SD duration met, otherwise, NE 
NE	NE 	NE 

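### The 12-week minimum for stable disease has no tolerance, so a compliant first scan on days 77–83 cannot support SD and best overall response can become PD or not evaluable because of when the scan was booked

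*Combined protocol and SAP*

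**What the plan says.** Section 2.4.2.1 defines best overall response, for RECIST 1.1 and irRECIST alike, and adds that SD counts only when measurements "met the SD criteria at least once after study entry at a minimum interval of 12 weeks from initiation of treatment". Section 6.7.4.1 repeats the condition ("measurements must have met the SD criteria at least once after study entry at a minimum interval of 12 weeks from initiation of treatment"). Neither place gives a tolerance.

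The timing of the first on-treatment scan comes from three statements:

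- Section 6.1, footnote 2: "Treatment cycles are to be repeated every 42 days until progression".
- Section 6.3.5: tumor evaluation takes place "on cycles 3, 5, 7, etc".
- Section 6.1, footnote 5: "Repeat tumor imaging every 12 weeks (+/- 1 week". Section 6.3.5 gives the same interval and window.

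The table in 6.7.4.1 shows what happens when the SD minimum is not met. In the rows CR then SD, CR then PD, and PR then PD, the result is "SD provided minimum criteria for SD duration met, otherwise, PD". In the rows CR then NE and PR then NE, the fallback is NE. No row begins with SD.

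Section 4.1.1 gives a different imaging frequency: "Subjects will undergo disease evaluation every 6 weeks for the first year".

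**The concern.** The SD threshold sits exactly on the nominal day of the first scan, while the schedule lets that scan be taken up to seven days earlier. Two subjects with the same tumor course, one scanned on day 80 and the other on day 84, can receive different best overall responses.

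Best overall response by both criteria is the first-listed secondary objective (2.2.1). The shift goes only downward, from SD to PD or NE. If a tolerance is intended but not written, someone will have to decide on it once the data are in view.

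**Working it through.** **1. Nominal day of the first scan.** Inputs: 42-day cycles (6.1, footnote 2) and first on-treatment scan at Cycle 3 (6.3.5). Two completed cycles give 2 × 42 = 84 days after Cycle 1 Day 1, and 84 / 7 = 12.0 weeks. This reproduces the plan's 12-week interval. It also equals the SD minimum of 12 × 7 = 84 days, so there is no slack.

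**2. Permitted scan days against the SD minimum.** The imaging window is 84 ± 7, that is days 77 to 91, or 15 days. Days 77 to 83 fall short of 84: 7 of 15, or 46.7%. If the general visit window were used instead ("A window of +/- 3 days applies to all study visits unless otherwise specified"), the range would be days 81 to 87, and 3 of 7 days would still fall short.

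**3. Whether a later scan rescues the subject.** The next scheduled scan is at 24 weeks, 168 ± 7, or days 161 to 175. After a first scan showing SD on, say, day 80:

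- next scan SD: the minimum is now met, so there is no loss;
- next scan PR or CR: the subject is a responder, so there is no loss;
- next scan PD: no qualifying SD exists, and PD follows if the table's rule is extended to SD-first sequences;
- next scan NE: no qualifying SD exists, and NE follows by the same extension.

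For a first scan showing CR or PR followed by PD or NE, the table states the fallback outright. The repeat scan used to rule out pseudoprogression (4.6 and 6.7.4) comes only after PD, so it cannot supply the missing SD.

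**4. Whether the 6-weekly schedule in 4.1.1 removes the problem.** It does not. A 12-week scan taken in week 11 still misses day 84, and PD could follow at about week 18.

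**5. What depends on the SD minimum.** The 12-week ORR (2.4.1) and the Simon rule (8.2) count CR and PR. PFS and OS (2.4.2.3, 2.4.2.4) run to progression or death. In the table rows at issue the result is SD, PD or NE, none of which is a response, so moving the minimum leaves the CR+PR best response rate unchanged.

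**6. Possible size.** The documents give no distribution of scan days and no SD or progression rates, so all three are assumptions. Number affected = 56 × (share with SD first) × (share of those progressing by the second scan) × (share of first scans before day 84).

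| Assumed SD first / then PD | No early scans | Spread evenly (7/15) | All early |
|---|---|---|---|
| 35% / 50%: 56 × 0.35 × 0.50 = 9.8 | 0 | 4.6 | 9.8 |
| 20% / 30%: 56 × 0.20 × 0.30 = 3.4 | 0 | 1.6 | 3.4 |

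These counts cover SD followed by PD only. SD followed by NE would add to them.

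**7. Effect of aligning the two rules.** With the minimum at 84 − 7 = 77 days, 0 of the 15 permitted days fail, against 7 now.

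**The case against.** The strongest reply is that little hangs on this. Section 8.4 reports response rates with Wilson intervals; no disease-control rate or SD rate is defined, tested or used in a decision. The shift from SD to PD or NE works against the regimen, so it cannot inflate apparent activity. A strict 12-week minimum is also a legitimate, conservative choice. All of this stands, and it limits the weight of the point. It does not remove the mismatch: a scan that the schedule permits still cannot satisfy the definition.

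Three stronger readings are tempting, and the documents do not support them.

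- *That PD is prescribed for SD followed by PD.* The table has no SD-first row. PD is inferred from the SD note together with the CR and PR rows.
- *That at least 5 subjects are affected.* This takes 47% early scans as a floor. That share holds only if scans are spread evenly over the window. The scan is listed among the Cycle 3 Day 1 assessments, and if every site scans on or after day 84 the number is 0. Nothing in the documents says that scans are booked ahead of the visit.
- *That the response endpoints are distorted.* A subject with PR on day 80 and PD at the next scan counts as a responder for the primary endpoint, yet the table gives a best overall response of PD. That is striking, but most of it comes from a separate conflict. The text of 2.4.2.1 and 6.7.4.1 takes the best response before progression, which is PR; the table gives SD or PD. Changing the SD minimum does not settle that conflict.

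**Conclusion.** The point holds as a mismatch between the SD definition and the imaging window: 7 of 15 compliant first-scan days cannot support SD, and neither imaging schedule in the protocol cures this. The consequence, PD or NE in place of SD, arises only when the next assessment is PD or NE. It is confined to the SD/PD/NE split of the descriptive best overall response by RECIST 1.1 and irRECIST.

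The size cannot be derived from the documents. With 35% SD first and half of those progressing by the second scan (both assumed), it runs from 0 through about 5 (scans spread evenly) to about 10 of 56 (all early), and is smaller at lower assumed rates. The point is worth correcting; it does not threaten the trial's main conclusion.

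**What to change.** In 2.4.2.1 and 6.7.4.1, apply the imaging window to the SD minimum, for example: *at least 12 weeks minus the 1-week imaging window (77 days) from initiation of treatment*. Add SD-first rows to the 6.7.4.1 table (SD followed by SD, PD and NE, and by PR and CR) using the same minimum, so that the outcome is stated and need not be inferred.

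Two related items should be reconciled separately: the 6-weekly evaluation in 4.1.1 against the 12-weekly imaging in 6.1 and 6.3.5, and the text against the table on best response when PR is followed by PD.

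The cost is one phrase in two places and a few table rows, with no change to visits, treatment or sample size. The downside is that SD may be assigned on up to one week less follow-up. If the strict 84-day minimum is preferred, the alternative is to require the first scan on or after day 84, which gives up the early half of the window.

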#### 4.7 Duration of Follow Up

Subjects will be followed for up to 3 years after removal from study treatment for determination of OS. Subjects removed from study treatment for unacceptable AEs will be followed for resolution or stabilization of the adverse event(s). All subjects (including those withdrawn for AEs) should be followed after removal from study treatment as stipulated in the protocol.

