### 8.4 Data Analysis Plans

ORRs and best response rates will be determined using both the RECIST 1.1 and irRECIST criteria will be reported along with their corresponding 95% confidence intervals. Wilson’s method will be used to calculate confidence intervals for these rates (reported as percentages). PFS and the duration of response estimates using both the RECIST 1.1 and irRECIST criteria will be calculated using the Kaplan-Meier (or product-limit) method. OS will also be calculated using the Kaplan-Meier (or product-limit) method. These time to event estimated functions will be plotted, and median time to estimates will be reported along with their 95%

confidence intervals. The confidence intervals for these time to event functions will be calculated using the standard and well known “loglog” method. If appropriate, 6, 12, and 24 month estimates for the time to event functions will also be reported.

The primary analysis will apply to the total number of evaluable subjects. Toxicity and safety information will be reported in a descriptive manner in the form of frequency tables. Toxicity will be defined through the number and frequency of treatment-emergent grade 3 and 4 toxicities as defined by National Cancer Institute - Common Terminology Criteria for Adverse Events (NCI CTCAE v4.03). Hypothesis generating exploratory analyses will be performed when appropriate sample size considerations allow. The definitions of the outcomes (or endpoints) of interest can be found in section 2.4.

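### Duration of response ends at progression only, so a responder who dies without documented progression is censored although the same death is a PFS event

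*Combined protocol and SAP*

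**What the plan says.** Section 2.4.2.5 defines duration of response twice, for RECIST 1.1 and for irRECIST, in the same terms. The clock starts at the first scan showing partial or complete response and runs "until the event of disease progression occurs. Any subject that has not had a documented progression at the time of analysis will be censored". Death is not mentioned either time.

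Section 2.4.2.3 treats death differently. PFS by RECIST 1.1 runs "until the event of disease progression occurs or death from any cause", and immune-related PFS runs "until the event of disease progression as defined by irRECIST, or death from any cause".

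Section 8.4 states that "PFS and the duration of response estimates using both the RECIST 1.1 and irRECIST criteria will be calculated using the Kaplan-Meier (or product-limit) method". It adds landmark figures: "If appropriate, 6, 12, and 24 month estimates for the time to event functions will also be reported". For definitions it sends the reader back: "The definitions of the outcomes (or endpoints) of interest can be found in section 2.4". The objective in section 2.2.5 and the response rules in section 6.7 add neither a death event nor a competing-risk method.

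**The concern.** A responder who dies without documented progression is an event for both PFS endpoints and a censored observation for both duration-of-response endpoints. Plain Kaplan-Meier then treats the dead responder as someone who could still have progressed later at the same rate as the others. The resulting curve is not time alive and in response. It is also not the observed proportion of responders who have progressed by a given time.

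The protocol itself makes such deaths plausible. Section 5.2.8 lists fatal pneumonitis, fatal colitis and fatal toxic epidermal necrolysis with nivolumab, so a responder can die of toxicity while in response. The Time and Events Table (section 6.1) has no tumor measurement at end of treatment or afterwards, so a responder who stops for toxicity may die with no progression on record.

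At stake is how a secondary, descriptive endpoint reads beside PFS: the same deaths shorten one and not the other.

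**Working it through.** **1. Definitions side by side**

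| Endpoint | Starts | Ends | Responder dies, no documented progression |
|---|---|---|---|
| PFS, RECIST 1.1 (2.4.2.3) | Day 1 | progression or death | event |
| PFS, irRECIST (2.4.2.3) | Day 1 | progression or death | event |
| Duration of response, both criteria (2.4.2.5) | first response scan | progression | censored |

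**2. Direction.** Suppose the dead are censored at the death date. Risk sets are then the same whether or not death counts; only the number of events differs. The as-written curve can therefore never lie below the curve that counts death, and the two coincide if no such death occurs. If the dead are censored at the last scan instead, risk sets change and this ordering is not guaranteed in every data set. The shift is still upward on average (step 4).

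**3. Size.** The plan states no figure for duration of response, so there is none to reproduce. Assumed inputs: constant independent hazards, a 6.0-month median time to progression or death, and a share f of first events that are deaths.

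- Total hazard λ = ln 2 / 6.0; progression hazard λ(1 − f).
- As-written median = 6.0 / (1 − f).
- As-written 12-month estimate = 0.5^(2(1 − f)); with death counted it is 0.5² = 25%.

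| f | Median (months) | Overstatement | 12-month estimate |
|---|---|---|---|
| 5% | 6.0/0.95 = 6.3 | 5% | 0.5^1.9 = 27% |
| 10% | 6.0/0.90 = 6.7 | 11% | 0.5^1.8 = 29% |
| 20% | 6.0/0.80 = 7.5 | 25% | 0.5^1.6 = 33% |
| 30% | 6.0/0.70 = 8.6 | 43% | 0.5^1.4 = 38% |

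A small invented example: 17 responders with event times 1 to 17. With all events counted, survival first falls below one half at time 9 (8/17 = 0.47). If the events at times 2, 5 and 8 are deaths and are censored, survival is (16/17)(13/15)(10/12)(7/9) = 0.53 at time 10 and (16/17)(13/15)(10/12)(6/9) = 0.45 at time 11. The median moves from 9 to 11.

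**4. Does last-scan censoring remove it?** No. In a simulation with progression read only at scans (6- or 12-week grid, ±1 week, same assumptions, scans continuing), the 12-month estimate is 27.1% to 27.9% with death counted. As written it is 29.6% to 40.1% with censoring at death and 29.4% to 39.2% with censoring at the last scan.

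**5. Against sampling error.** Responders: 17 at the success threshold in section 8.2, and 0.35 × 56 = 19.6, about 20, at the alternative rate. Over the range of f that is 17 × 0.05 = 0.9 to 20 × 0.30 = 6 deaths. The exponential 95% interval for a median of 6.0 with d events is 6.0 × 2d/χ²(0.975; 2d) to 6.0 × 2d/χ²(0.025; 2d). This gives 3.9 to 10.3 months (d = 17) and 4.0 to 9.8 months (d = 20), and 6.3 to 8.6 lies inside both. For a 12-month estimate of 25%, ±1.96 × √(0.25 × 0.75/17) is ±21 points, and with 20 responders ±19 points; 38% is 13 points away.

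**6. Deaths after scanning has stopped.** Sections 6.1 and 6.4 schedule no tumor imaging after treatment ends. A responder who stops without progression may progress unseen and die much later. Counting that death at its date credits the unseen interval as response. With f = 5% and an assumed 30% of responders ceasing scans early, simulated 12-month estimates with every death counted at its date are about 31% to 38%, depending on the set-up, against a true 25%. In the set-up giving 38%, last-scan censoring gave about 29%. Adding death without a late-death rule can therefore replace one upward bias with another.

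**7. Design.** The Simon figures in section 8.2 reproduce (6/32, then 17/56: exact alpha 0.0903, power 0.8012). They do not involve duration of response.

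**The case against.** The strongest reply is that the documents do not contradict themselves. PFS and duration of response are separate endpoints with separate, readable definitions, and nothing in the protocol says they must treat death alike. That stands: this is an analysis choice with a predictable bias, not an internal contradiction. Nor can a departure from the published response criteria be shown from these documents. What remains is that a progression-only measure under plain Kaplan-Meier needs either death as an event or a competing-risk method, and the plan has neither.

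The second reply is that every input to the size is assumed. That also stands. At f = 5% to 10%, about one or two deaths, the shift is only 0.3 to 0.7 months.

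A reader might infer something stronger: that the dead stay in the risk set until the analysis date, giving medians of 6.5 to 10.8 months, with the largest outside sampling error. The documents do not support this. Section 2.4.2.5 uses the time of analysis to say who lacks a documented progression; it sets no censoring date. Even on that reading, f = 30% leaves about 12 to 14 progression events (17 × 0.7 to 20 × 0.7). The interval around 6.0 months is then 3.7 to 11.6 or 3.8 to 11.0, and both contain 10.8.

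PFS also lacks a censoring date ("Any subject that has not had a documented event at the time of analysis will be censored"), but on its own that is only missing detail.

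**Conclusion.** The point holds as a recommended correction. As written, deaths without documented progression are censored in duration of response under both criteria, which biases the reported duration upward relative to time to progression or death whenever such deaths occur. Under death-date censoring the direction needs no assumption about how many there are. The size does: 6.3 to 8.6 months instead of 6.0, and 27% to 38% instead of 25% at 12 months, rest on constant independent hazards, an assumed 6.0-month median and an assumed death share of 5% to 30%. With 17 to 20 responders these shifts are within sampling error, so the argument is that a one-directional bias can be removed by definition, not that the result would be visibly wrong.

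A reader might carry this over to the efficacy decision. That would be mistaken: ORR, the sample size and the Simon rule do not use this endpoint.

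**What to change.** In section 2.4.2.5, for both criteria:

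- Define duration of response as the time from first documented response to documented progression or death, whatever the cause, whichever comes first.
- Censor responders with neither event at the last adequate tumor assessment.
- State in the definition how deaths long after the last adequate scan are handled. One option is censoring at the last adequate assessment once a pre-set number of assessments has been missed. Report the alternative handling as a sensitivity analysis.

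If a progression-only measure is intended, call it time to progression among responders and report the cumulative incidence of progression with death as a competing risk.

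The cost is a few sentences and no new data, because deaths are already collected: "Subjects will be followed for up to 3 years after removal from study treatment for determination of OS" (section 4.7). The downsides are that medians may be somewhat shorter and that the late-death cut-off has to be chosen before the data are seen.
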